### **3.2 SAMPLE SIZE AND POWER ESTIMATES**

The risk of preterm birth < 37 weeks gestation in untreated nulliparous women was estimated to be about 8.0% for the EAGeR trial. Unpublished data for 2012 from the GN sites show preterm birth rates, ranging from 2.9% to 9.8%, while WHO estimates the range for the countries in which GN sites are located to be 7.7% to 16.7%. In developing sample size estimates we considered risks in the range of 8% to 14% and ultimately selected sample sizes based on a conservative estimate of 8%. Because the association of LDA and preterm birth may differ in international settings, we examined sample size requirements for reductions of 40%, 25%, and 20%. As shown in **Table 2** below, the number of evaluable participants needed to detect a 20% reduction from a usual rate of 8% preterm births with 90% power is 5,483 per treatment arm. To account for the loss of evaluable subjects due to miscarriages, which are anticipated to occur in approximately 5% of participants) and loss to follow-up (assumed to be in the 1% to 2% range), sample sizes were increased by 8% to obtain a final sample size of 11,920 (or 5,960 per treatment arm).

The Global Network has access to approximately 68,000 births per year. It is estimated that 40% would be nulliparous, yielding 23,800 potential pregnancies per year. With an enrollment rate of one third of eligible women, this trial could easily be accomplished by the Global Network within an 18 month enrollment period.

**Table 2. Evaluable Sample Size Estimates**

PTB rate in Placebo Arm	PTB rate in ASA	% Red	Sample size per group	PTB rate in ASA	% Red.	Sample size per group	PTB rate in ASA	% Red.	Sample size per group
Power=80% ( $\alpha=0.05$ ; $\beta=0.2$ )									
8%	4.8%	40%	918	6.0%	25%	2,554	6.40%	20%	4,096
10%	6.0%	40%	721	7.5%	25%	2,005	8.00%	20%	3,213
12%	7.2%	40%	591	9.0%	25%	1,638	9.60%	20%	2,625
14%	8.4%	40%	497	10.0%	25%	1,377	11.20%	20%	2,204
Power=90% ( $\alpha=0.05$ ; $\beta=0.1$ )									
8%	4.8%	40%	1,228	6.0%	25%	3,419	6.40%	20%	5,483
10%	6.0%	40%	965	7.5%	25%	2,683	8.00%	20%	4,301
12%	7.2%	40%	790	9.0%	25%	2,193	9.60%	20%	3,513
14%	8.4%	40%	665	10.5%	25%	1,842	11.20%	20%	2,950

**Sample Size—Secondary Outcomes:** One of the key secondary objectives of this trial is to evaluate the effect of low dose aspirin on perinatal mortality. We evaluated the reduction in perinatal mortality that could be detected with 80% power and 90% power under the assumption that the sample size for the study would be based on that needed to achieve the primary aim of demonstrating a 20% reduction in low-birth weight infants. The analyses were based on the assumption that the perinatal mortality rate in the GN population is approximately 45 perinatal deaths per 1000 deliveries (unpublished data from the MNH Registry for 2013). With this estimated underlying mortality rate and 5,483 evaluable subjects per treatment arm required to demonstrate the 20% reduction in low birth weight prevalence as outlined in the primary aim, the study will have 80% power to detect a 24% reduction in perinatal mortality and 90% power to detect a 27% reduction in perinatal mortality.

To determine the sample size actually needed to demonstrate the reduction in perinatal mortality actually expected if the intervention results in a 20% reduction in prevalence of low birth weight infants, we examined both the prevalence of low birth weight infants across the GN sites and the perinatal mortality risk in both the low birth weight and normal birth weight infants. Based on 2013 MNH Registry data, the prevalence of low birth weight among all GN deliveries was 16.3% and the perinatal mortality rates were 20.5 per 1000 deliveries among normal birth weight infants and 162.3 per 1000 deliveries among low birth weight infants; these values yield a weighted average perinatal mortality rate of 43.6 per 1000 deliveries. If the low dose aspirin intervention is effective in reducing the prevalence of low birth weight deliveries by 20% (i.e. reducing the prevalence from 16.3% to 13%) and the conditional risk of perinatal mortality is unchanged in the low birth weight and normal birth weight cohorts, we would expect the resultant overall perinatal mortality rate to be reduced to 38.9 per 1000 deliveries or a 10.8% reduction. Detection of a reduction of this magnitude with 80% power would require an evaluable sample size of greater than 28,000 evaluable deliveries per treatment arm, and the study would need over 37,000 evaluable deliveries per arm to achieve 90% power to detect a reduction of this level in perinatal mortality.

Given the sample sizes associated with the second approach, the best alternative appears to be to power the study to demonstrate the 20% reduction in prevalence of low birth weight deliveries with a commitment to generate point and interval estimates of the impact of the intervention on perinatal

mortality. By examining the risk of perinatal mortality in both the normal and low birth weight infants in the two arms, the trial would provide some insight about impacts of the intervention on mortality other than that mediated through the effect on birth weight.

We also conducted power analyses to examine the effect sizes that could be detected with the planned sample sizes for two additional secondary outcomes, prevalence of SGA infants and incidence of eclampsia/preeclampsia in the target population. Generic information as well as preliminary information from the 2013 MNH Registry indicates that the risk of each of these events in the population of interest is approximately 5%. Under the assumption of 5483 evaluable participants in each treatment arm and an assumed Type I error rate of 0.05 for per-comparison analyses (i.e. no control for multiple comparisons in the analyses of these secondary outcomes), the study will have 70% power to detect a 20% reduction in the risk of each of these outcome measures, 85% power to detect a 24% reduction and 90% power to detect a 26% reduction. Consequently, the study is reasonably powered to examine these secondary outcome measures.

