Given the sample sizes associated with the second approach, the best alternative appears to be to power the study to demonstrate the 20% reduction in prevalence of low birth weight deliveries with a commitment to generate point and interval estimates of the impact of the intervention on perinatal mortality. By examining the risk of perinatal mortality in both the normal and low birth weight infants in the two arms, the trial would provide some insight about impacts of the intervention on mortality other than that mediated through the effect on birth weight.

We also conducted power analyses to examine the effect sizes that could be detected with the planned sample sizes for two additional secondary outcomes, prevalence of SGA infants and incidence of eclampsia/preeclampsia in the target population. Generic information as well as preliminary information from the 2013 MNH Registry indicates that the risk of each of these events in the population of interest is approximately 5%. Under the assumption of 5483 evaluable participants in each treatment arm and an assumed Type I error rate of 0.05 for per-comparison analyses (i.e. no control for multiple comparisons in the analyses of these secondary outcomes), the study will have 70% power to detect a 20% reduction in the risk of each of these outcome measures, 85% power to detect a 24% reduction and 90% power to detect a 26% reduction. Consequently, the study is reasonably powered to examine these secondary outcome measures.

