Birth weight < 2500g	Binary	
The unit of analysis will be the individual infant and per the protocol, the event is defined as: “Birth weight is defined as the first weight of the fetus or newborn obtained after birth. For live births, birth weight should preferably be measured within the first hour of life before significant postnatal weight loss has occurred, recorded to the degree of accuracy to which it is measured (WHO). Birth weight <2500 g is defined as low birth weight” This outcome measure will be a derived measure obtained using the birth weight information provided on Questions C3-C5 from Form MN02 from the MNH Registry. If the actual measure is obtained, the binary variable will be generated from Question C3; otherwise it will be based on the response to Question C5.
 
For any outcomes involving birth weight, the reported weight will only be used to calculate that outcome if collected within 4 days of birth. Any weight captured after 4 days will be excluded.
 
Analysis population: mITT

Variable	Type	Definition
Birth weight < 1500g	Binary	
The unit of analysis will be the individual infant and per the protocol, the event is defined as: "Birth weight is defined as the first weight of the fetus or newborn obtained after birth. For live births, birth weight should preferably be measured within the first hour of life before significant postnatal weight loss has occurred, recorded to the degree of accuracy to which it is measured (WHO). Birth weight <1500 g is defined as very low birth weight." This outcome measure will be a derived measure obtained using the birth weight information provided on Questions C3-C5 from Form MN02 from the MNH Registry. If the actual measure is obtained, the binary variable will be generated from Question C3; otherwise it will be based on the response to Question C5.
 
For any outcomes involving birth weight, the reported weight will only be used to calculate that outcome if collected within 4 days of birth. Any weight captured after 4 days will be excluded.
 
Analysis population: mITT

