## 9.5 Secondary Outcome Analyses

This study has been designed to evaluate the differences between the two treatment arms for three secondary outcomes: the risk of perinatal mortality; the risk of eclampsia/preeclampsia, and the risk of a SGA delivery. As with the primary analyses, each of these outcomes will be examined individually using descriptive tests of hypotheses that the risk differs between the two arms based on Cochran-Mantel-Haenszel tests stratified by Global Network sites. The analyses for each of these 3 secondary outcomes will utilize the same modified intention-to-treat population used for the primary outcome. Each of these hypothesis tests will be conducted at the 0.05 level of significance with no adjustment for multiple comparisons. In addition to this set of hypothesis tests, model-based analyses comparable to those conducted for the primary analyses will be used to evaluate potential heterogeneity of treatment effect across sites and evaluate potential confounding. For each of the 3 outcomes, an initial model will include terms for treatment, site, and a treatment by site interaction. If the treatment by site interaction term is found to be significant ( $p<0.05$ ), then all subsequent models will include the interaction term and all effects will be reported by site; because the study will lack power to detect site-specific effects, all p-values will be reported for the average effect and site effects will include point and interval estimates. If the interaction term is not significant, it will be removed from the model and this initial model be used to estimate an unadjusted treatment effect controlling for site. The second series of models will include any demographic or clinical variable found to differ significantly between the treatment arms in the preliminary analyses described above. These models

will be used to generate adjusted estimates of the treatment effect controlling for potential confounders.

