Table 3a: Medication Compliance by Site – MITT Population

GN Site	Enrolled N	Level of compliance					
		Total Dosed N	< 30% N (%)	30-50% N (%)	50-70% N (%)	70-90% N (%)	> 90% N (%)
GN02: DRC							
GN03: Zambia							
GN06: Guatemala							
GN08: India (Belagavi)							
GN09: Pakistan							
GN11: India (Nagpur)							
GN12: Kenya							

Table 4: Reasons for Medication Noncompliance – MITT Population

Measures of Non-Compliance	Placebo	Aspirin
Number of Biweekly Visits N		
Visits where pills not taken as instructed, N (%)		
Reasons for Noncompliance, N (%)		
Another person took pills		
Pills were lost		
Pills made me feel sick		
Forgot to take pills		
Travelled and did not bring pills		
Didn't understand instructions for pills		
Pills were destroyed		
Other		

Table 5a: Primary and Secondary Efficacy Outcomes

	Placebo N = XXXX	Aspirin N = XXXX	p-value	Unadjusted RR (95% CI)	Adjusted RR (95% CI)
Primary Outcome, N included					
Preterm Delivery, N (%)					
Secondary Efficacy Outcomes					
Hypertensive Disorders, N (%)					
Small for Gestational Age, N (%)					
Perinatal Mortality, N (%)					
Other Maternal Outcomes of Interest					
Vaginal bleeding, N (%)					
Antepartum hemorrhage, N (%)					
Postpartum Hemorrhage, N (%)					
Maternal mortality through 42 days, N (%)					
Late Abortion, N (%)					
Preterm Preeclampsia, N (%)					
Other Fetal Outcomes of Interest					
Preterm birth <34 0/7 weeks of pregnancy, N (%)					
Birth weight < 2500g, N (%)					
Birth weight < 1500g, N (%)					
Fetal Loss, N (%)					
Spontaneous abortion, N (%)					
Stillbirth, N (%)					
Medical Termination of Pregnancy (MTP), N (%)					

*NOTE: Table contains outcomes summarize using MITT population as well as outcomes summarized using ITT population. Final table will clearly identify which population is used for each outcome. Birth weight will be summarized both including and excluding estimated weights. Adjusted RR will not be presented in primary paper. Footnotes will be included to describe p-value is from CMH test as well as models used to obtain RR estimates.*

Table 5b: Primary and Secondary Efficacy Outcomes by Site

*NOTE: Table will also include fetal outcomes of interest.*

Outcome Measure	Risk of Outcome			
	Placebo N = XXXX	Aspirin N = XXXX	RR (95% CI)	p-Value
Preterm Delivery, N (%)				
GN01: DRC				
GN03: Zambia				
GN12: Kenya				
GN06: Guatemala				
GN08: Belagavi				
GN11: Nagpur				
GN09: Pakistan				

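### The sample-size text names low birth weight, not preterm birth, as the aim that 5,483 per arm serves, and reads mortality within birth-weight groups in a way a randomized comparison cannot support

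*Combined protocol and SAP*

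**What the plan says.** Preterm birth is the primary outcome in Protocol 2.5 and SAP 3.1. Protocol 3.2 sizes the trial on it: the number "needed to detect a 20% reduction from a usual rate of 8% preterm births with 90% power is 5,483 per treatment arm". Birth weight below 2,500 g is listed only among the other fetal outcomes (Protocol 2.7, SAP 3.3).

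The secondary-outcome paragraphs of Protocol 3.2, repeated in SAP 6.2, speak instead of "5,483 evaluable subjects per treatment arm required to demonstrate the 20% reduction in low birth weight prevalence as outlined in the primary aim". They conclude that the best course is to "power the study to demonstrate the 20% reduction in prevalence of low birth weight deliveries", with a commitment to point and interval estimates for perinatal mortality. One further sentence proposes a breakdown: "By examining the risk of perinatal mortality in both the normal and low birth weight infants in the two arms". Its purpose concerns mechanism and is worded softly. What the authors hope to gain from it is "some insight about impacts of the intervention on mortality other than that mediated through the effect on birth weight".

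SAP 9.5 examines perinatal mortality in the mITT population by testing whether "the risk differs between the two arms based on Cochran-Mantel-Haenszel tests stratified by Global Network sites". The Table 5a shell has one row, "Perinatal Mortality, N" (%), and Table 5b splits it by site. Neither has a birth-weight grouping.

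**The concern.** Two statements are wrong as written. First, the sample-size attribution contradicts the trial's own calculation and its own primary outcome.

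Second, the sentence on birth-weight groups gives a reading that the comparison cannot carry. The surrounding scenario assumes that aspirin moves infants from below to above 2,500 g. If it does, the low-birth-weight group on aspirin holds different infants from the low-birth-weight group on placebo, and so does the normal-weight group. Differences between arms within a group then mix any treatment effect with this change in membership. A reader who follows the sentence could take an apparent excess of deaths among small or normal-weight infants on aspirin as an effect outside the birth-weight pathway when no such effect exists.

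**Working it through.** **Inputs.** From Protocol 3.2 and SAP 6.2: preterm birth 8.0% to 6.4%; low birth weight 16.3% to 13%; perinatal mortality 162.3 (low) and 20.5 (normal) per 1,000; 5,483 per arm. From SAP 7.5: two-sided 5% level.

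**1. What 5,483 is for.** For two proportions, n = [1.960·√(2·p̄(1−p̄)) + 1.282·√(p1(1−p1) + p2(1−p2))]² / (p1−p2)².

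- Preterm birth, 0.080 and 0.064: (0.716 + 0.468)² / 0.016² = 5,483, the plan's figure exactly. Then 5,483/0.92 = 5,960 per arm, also as stated.
- Low birth weight, 0.163 and 0.130: (0.980 + 0.640)² / 0.033² = 2,411.

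**2. The plan's mortality projection.**

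- Placebo: 0.163×162.3 + 0.837×20.5 = 43.6 per 1,000.
- Aspirin, group rates unchanged: 0.13×162.3 + 0.87×20.5 = 38.9 per 1,000.

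Both match the documents. In this scenario both within-group RRs are 1.00 and the overall RR is 0.89.

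**3. Low birth weight falls to 13% and no infant's survival changes.** Let r be the mortality per 1,000 of the 3.3% of infants moved across 2,500 g. The documents do not give r, so it is varied between the two group rates.

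- Low group on aspirin = (0.163×162.3 − 0.033·r)/0.13
- Normal group on aspirin = (0.837×20.5 + 0.033·r)/0.87

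The overall rate is 43.6 in both arms for every r, so overall RR is 1.00. With 5,483 per arm the groups hold 894 against 713 infants (low) and 4,589 against 4,770 (normal), placebo against aspirin. The chance of a nominal p<0.05 in the direction of excess on aspirin is 1 − Φ[(1.960·s0 − d)/s1], where d is the difference in risk, s0 the pooled and s1 the unpooled standard error. For the low group at r=60, d=0.0260, s0=0.0190 and s1=0.0191, which gives 28%.

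| r | Low group on aspirin | RR low | Normal group on aspirin | RR normal | Chance low | Chance normal |
|---|---|---|---|---|---|---|
| 20.5 | 198.3 | 1.22 | 20.5 | 1.00 | 47% | 2.5% |
| 60 | 188.3 | 1.16 | 22.0 | 1.07 | 28% | 7% |
| 100 | 178.1 | 1.10 | 23.5 | 1.15 | 13% | 17% |
| 162.3 | 162.3 | 1.00 | 25.9 | 1.26 | 2.5% | 41% |

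The larger of the two RRs is smallest near r=85, where both are 1.12. With a 10% reduction in low birth weight (16.3% to 14.67%), the largest RRs are 1.10 (low) and 1.13 (normal), and no chance exceeds about 14%.

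**4. A benefit that runs wholly through birth weight.** If the moved infants' mortality falls from 60 to 20.5, the overall rate is 0.13×188.3 + 0.87×20.5 = 42.3 (RR 0.97). The low group still shows RR 1.16, although no non-mediated effect exists.

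**5. The same deaths as joint outcomes.** At r=60 under step 3, per 1,000 of all deliveries: placebo 26.5 (low) + 17.2 (normal), aspirin 24.5 + 19.1. Before rounding, each pair sums to 43.6, so the shift between groups is visible as a shift.

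**The case against.** The strongest reply is that this is one soft sentence in a sample-size rationale. It offers only some insight and specifies no ratio, test or mediation model. The explicit commitment is to overall point and interval estimates, which SAP 9.5 and Table 5a provide. SAP 7.5 makes secondary analyses exploratory. All of that stands, and it limits the weight of the point.

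Four stronger readings are tempting, and the documents do not support them:

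- A reader might infer that the trial is mis-sized or that low birth weight is really primary. Preterm birth is primary in every defining section, and 5,483 is correct for it.
- A reader might infer a broken promise because SAP Section 9 omits the breakdown. No analysis was committed to, and SAP 2 allows further exploratory analyses under abbreviated plans. With no table shell for it, a report of harm is a possibility and not a planned output.
- A reader might infer that deaths without a measured weight cannot be placed. The birth-weight entries in SAP 9.2 say "Any weight captured after 4 days will be excluded", but they also fall back from Question C3 to Question C5 when no actual measure exists, and the Table 5a note covers estimated weights. Only deaths still unclassified after that rule lack a place, and their number is not given.
- A reader might infer that a false signal is close to an even chance. The 47% and 41% figures need r at exactly one end of its range.

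It is also fair that the plan's own scenario, with group-specific mortality unchanged, gives within-group RRs of 1.00. When aspirin acts only on the moved infants, that requires them to average 162.3 per 1,000 before the move and 20.5 after it. The trial cannot identify these infants, so it cannot verify this.

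**Conclusion.** The point holds in two parts. The attribution of 5,483 to low birth weight is an error of wording: the figure belongs to preterm birth, and low birth weight on the documents' rates would need about 2,411. The stated reading of mortality within birth-weight groups is wrong in method: with no effect on any infant's survival the within-group RR can be as high as 1.22 (low) or 1.26 (normal), and which group shows the excess depends on a quantity the trial does not observe.

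These sizes assume that the 2013 registry rates for all deliveries apply to nulliparous participants, that low birth weight falls by the full 20%, and that r lies between 20.5 and 162.3. A smaller reduction shrinks them. The primary test, the sample size and the overall mortality analysis are not affected. The change should be made because the sentence would mislead if followed and is cheap to correct.

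**What to change.** Before unmasking, which SAP 4.4 places after data lock:

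1. In the secondary-outcome text of Protocol 3.2 and SAP 6.2, name preterm birth (8.0% to 6.4%) wherever the primary aim or the purpose of 5,483 is stated. Label the low-birth-weight mortality calculation a separate scenario.
2. Delete the sentence on non-mediated effects. If a birth-weight breakdown is wanted, define it in SAP 9.5 or in an abbreviated plan under SAP 2 as descriptive joint outcomes over all mITT deliveries: death with weight below 2,500 g, death with weight of 2,500 g or more, and death with weight unknown after the Question C3/C5 rule. State that it carries no mediation reading.

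The cost is wording in two sections and either one sentence removed or three descriptive rows added. It needs no new data and leaves the sample size, the primary analysis and the overall mortality analysis as they are.

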### **3.3 AVAILABLE POPULATION**

The sites of the Global Network have access to approximately 68,000 deliveries annually with 24,000 being potentially eligible pregnancies for this study. This diverse pregnant population is highly accessible and one which, in our international experience, has been eager to participate in non-invasive studies to promote the well-being of both mother and child. The Global Network sites estimate that as few as one third and as many as one half of eligible women will enroll in this protocol, which will allow the study to meet recruitment goals within 18 months.

### **3.4 PROJECTED RECRUITMENT TIME**

Each site will begin recruitment after their site-specific regulatory approvals are in place, the site has been adequately prepared, and training is completed. This will require a staggered start, as the timeline for these activities will vary per site. The projected timeline for this study is approximately 3 years (36 months). This includes a 12 month preparatory phase with 3 months for training, an 18 month recruitment period, and 6 months for data cleaning and analysis. A detailed study timeline is found in **Appendix 4**.

